### 9.3 Objective 3 Analysis Plan

**Objective 3:** Identify the mechanisms that explain the causal treatment effects.

The primary analysis for the exploratory objective 3 (specific aim 2) will involve a series of mediation analyses in order to identify the mechanisms that underlie the differential treatment responses. This analysis will use light phenotyping data from T2 and the interim assessment conducted at the midpoint of the first-stage treatment period. Second-treatment stage data will not be used for this analysis. Investigators did not propose a light phenotyping-based mediator for the Duloxetine treatment. Thus, a mediation analysis based on light-phenotyping data will not be carried out for this study arm.

The study does not include a control group since each of the four therapies have been previously shown to be effective for treating cLBP. As a result, the mediation analyses will be conducted by treatment group. Within each treatment group, the proposed treatment modifier will play the role of the exposure in the mediation analysis. Hypothesized mediators were determined by the study investigators and are listed in Table 6 by treatment arm.

For example, consider the PT/Exercise treatment group. Investigators expect that individuals who both receive the PT/Exercise treatment and have lower self-perception of their own efficacy will respond better to the PT/Exercise intervention and have lower PROMIS Pain Interference scores at follow up. They believe that this effect is attributable in part to changes in the patients fear avoidance beliefs and avoidance behaviors. The mediation analysis will assess whether greater pain catastrophizing is associated with a greater reduction in fear avoidance beliefs, which leads to greater improvement in pain interference scores.

The outcome measure for each mediation analysis will be the PROMIS Pain Interference score measured at T3. The exposures and mediators will be measured at T2 and the first treatment-stage midpoint, respectively.

*Table 6 Hypothesized Mediation Analyses by Treatment.*

Treatment	Mediation Analysis Exposure (X)	Expected treatment mediator (M)
MBSR	PROMIS Pain Catastrophizing	Experiences Questionnaire Score
PT/Exercise	Pain Self-Efficacy Score	Fear Avoidance Beliefs Questionnaire
Acupressure	Fibromyalgia Screening Score	GSS-8

Here we present the generic model that will be used in each mediation analysis. Figure 3 shows a graphical representation of the model. Let  $Y_i$  denote the T3 PROMIS pain interference score for the  $i^{th}$  subject in a single treatment arm. Let  $X_i$  and  $M_i$  denote the  $i^{th}$  subject's measurements of corresponding exposure and mediator, measured at T2 and the first treatment stage midpoint, respectively. Note that both  $X_i$  and  $M_i$  depend on the treatment arm. The vector  $W_i$  contains the baseline covariates: sex, age, BMI, race, and education.

We propose the following linear models for  $M_i$  and  $Y_i$  for all  $i = 1, \dots, n$ :

[figure not shown]
$$M_i = \alpha_0 + \alpha_1 X_i + \phi_1^T W_i + \epsilon_{1i}$$

$$Y_i = \beta_0 + \beta_1 X_i + \beta_2 M_i + \phi_2^T W_i + \epsilon_{2i},$$

and  $Cov((\epsilon_{1i}, \epsilon_{2i})^T | X_i, M_i, W_i) = \sigma^2 I$ .

For this model, the so-called indirect and direct effects of  $X_i$  on  $Y_i$  are equal to  $\tau_I = \alpha_1 \beta_2$  and  $\tau_D = \beta_1$ . The “total effect” equals the sum of the indirect and direct effects:  $\tau = \tau_I + \tau_D$ . Whether the intermediary variable  $M$  mediates the association between  $X$  and  $Y$  is determined by assessing the evidence against the null hypothesis that the indirect effect  $\tau$  equals 0. The mediation models will be fit in R using the *mediation* package. Inference for the indirect effect will be performed by creating a 95% confidence interval for both the direct and indirect effects using bias-corrected and accelerated bootstrapping. Confidence intervals for the proportion of the total effect mediated by  $M$  will also be produced.

Figure 3 Graphical representation of the mediation models. In all analyses Y represents a patients PROMIS Pain Interference Score, while X and M depend on treatment arm.

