## 7.3 Covariates and Subgroups

Since the purpose of the study is to identify patient subgroups that differentially respond to the four treatments, our analysis will explore many treatment-covariate interactions. Table 2 and 3 list the expected treatment modifiers, which are the primary covariates of interest, for the light and deep phenotype measures, respectively. The light phenotype table also describes each variable's expected mechanistic role (treatment modifier versus treatment mediator). For additional details, please see Section 18.1 of the UM BACPAC clinical trial protocol.

Table 2 Hypothesized light-phenotyping treatment modifiers.

Phenotypic variable	Expected treatment-phenotype interaction	Mechanistic Role
Patient pain catastrophizing score	MBSR	Moderator
Patient experience score	MBSR	Mediator
Fear avoidance beliefs score	PT/Exercise	Mediator
PROMIS self-efficacy score	PT/Exercise	Moderator
Fibromyalgia Screening Questionnaire	Acupressure	Moderator
Biologic Sex	Acupressure	Moderator
Fibromyalgia Screening Questionnaire	Duloxetine	Moderator
PainDETECT score	Duloxetine	Moderator

Table 3 Hypothesized deep-phenotyping treatment modifiers.

Deep Phenotype variable	Measurement Modality	Expected treatment-phenotype interaction	Mechanistic Role
Subgenual ACC activity	fMRI	MBSR	Moderator
Ventrolateral PFC activity	fMRI	MBSR	Moderator
S1 activity	fMRI	MBSR	Moderator
Thalamus activity	fMRI	MBSR	Moderator
Baseline activity	Actigraphy	PT/Exercise	Moderator
Parasympathetic tone	Heart Rate Variability	PT/Exercise	Moderator
Vagal Tone	EKG and PPG	PT/Exercise	Mediator

High Basal Inflammation	Blood Sample	PT/Exercise	Moderator
Pain Threshold	QST	Acupressure	Moderator
Posterior Insula Glutamate	H-MRS	Acupressure	Moderator
Insula-DMN connectivity	fMRI	Acupressure	Moderator
DMN-SI connectivity	fMRI	Acupressure	Moderator
Deficient Lower Back Pain Inhibition	QST	Duloxetine	Moderator
Lesser PAG-Insula connectivity	fMRI	Duloxetine	Moderator
Elevated Stimulated inflammatory response	Blood Sample	Duloxetine	Moderator

We plan to conduct a single subgroup analysis that will assess whether males and females differentially respond to the proposed treatments.

In addition to the covariates listed above, the following biological variables will be controlled for in the primary analysis: sex, age, BMI, race, and education.

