#### 9.1.1 Light Phenotyping Analysis

Let  $Y_{ti} \in \mathbb{R}$  denote subject  $i$ 's PROMIS pain interference score at time  $t \in \{2, 3, 4\}$ . Let  $R_i$  denote response status at T3. Let  $A_{ti}$  be a vector denoting treatment assignment, such that the first through 4th elements represent PT/Exercise, MSBR, Acupressure, and Duloxetine treatment status. The vector  $X_{2i}$  contains the baseline covariates for subject  $i$  at time 2 (sex, age, BMI, race, and education) and  $Y_{2i}$ . For  $t \in \{2, 3\}$ , the matrix  $Z_{ti}$  will hold subject  $i$ 's time  $t$  measurements of the hypothesized treatment modifiers.  $Z_{ti}$  will have 7 total columns that correspond to the hypothesized treatment modifiers, and the columns will be specified such that the element-wise product  $A_{ti} \cdot Z_{ti}$  represents the 8 hypothesized treatment-phenotype interactions.

We jointly model data at T3 and T4 to gain efficiency in estimating the main effects of treatment, the main effects of the potential moderators, and the interaction effects between treatment and the potential moderators in stage 1. The main effects of treatment and covariates are allowed to differ between stages, but we assume these effects are additive. In contrast, treatment-by-phenotype interaction effects are assumed to be the same across both stages. We propose the following model:

$$\begin{aligned} E[Y_{3i}] &= X_{2i}^T \beta_2 + A_{2i}^T \phi_2 + Z_{2i}^T \varphi_2 + (A_{2i} \circ Z_{2i})^T \psi_2 \\ E[Y_{4i}] &= X_{2i}^T \beta_2 + A_{3i}^T \phi_2 + Z_{3i}^T \varphi_2 + R_i^T [A_{3i}^T \phi_{3R} + Z_{3i}^T \varphi_{3R}] \\ &\quad + (1 - R_i)^T [A_{3i}^T \phi_{3NR} + Z_{3i}^T \varphi_{3NR}] + (A_{3i} \circ Z_{3i})^T \psi_2 \end{aligned}$$

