## 9.2 Objective 2 Analysis Plan

**Objective 2:** Identify additional predictors of differential treatment response using light phenotype data.

This exploratory analysis will assess whether additional patient reported outcomes captured in clinical settings can improve the prediction of differential treatment response. First, we will assess the functional forms of the predictors through univariate summaries and assess multicollinearity through pairwise Spearman correlation coefficients. Then, we will fit regularized regression models for the primary pain outcome (PROMIS pain interference score) using observations from time points T3 and T4. We will utilize adaptive elastic net (AENET) to induce variable selection while accommodating groups of correlated predictors. Given the exploratory nature of this objective, that

trial patients may have just failed other treatments prior to entering the study, and the need for as much data as possible for the proposed methods, we will treat observations from time points T3 and T4 as independent rather than as repeated measures and adjust for potential effects of stage 1 treatment on observations at T4. We will consider the selection of a treatment interaction into the model as weak evidence for treatment effect modification, and we will conduct hypothesis testing for strong evidence of treatment effect modification. The analysis will be repeated for the secondary pain outcomes (Pain Intensity (PEG) and Patient Global Impression of Change (PGIC)).

Let  $Y_{ti} \in \mathbb{R}$  denote subject  $i$ 's PROMIS pain interference score at time  $t \in \{2, 3, 4\}$ ,  $R_i$  denote response status at T3,  $A_{ti}$  be a vector denoting treatment assignment for  $t \in \{2, 3\}$ , and  $X_{2i}$  denote the vector of baseline variables for subject  $i$  at time point T2 (sex, age, BMI, race, education, and the baseline outcome). Let  $Z_{ti}$  be a vector denoting the additional (clinical/patient reported) predictors and their treatment interactions for subject  $i$  and  $t \in \{2, 3\}$ . We assume

$$E[Y_{ti}] = X_{2i}^T \beta + A_{(t-1)i}^T \phi + I(t = 4) * [R_i A_{2i}^T \varphi_R + (1 - R_i) A_{2i}^T \varphi_{NR}] + Z_{(t-1)i}^T \gamma,$$

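### The mediation equations in SAP 9.3 omit the T2 mediator and T2 pain interference, so they do not estimate the change hypothesis stated there, and the bias can go either way

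*SAP*

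**What the plan says.** SAP 9.3 (Objective 3) runs one mediation analysis within each of three arms: MBSR, PT/Exercise and acupressure. The exposure X is measured at T2, the mediator M at the midpoint of the first treatment period, and the outcome Y is PROMIS Pain Interference at T3. M is regressed on X and W, and Y on X, M and W. W "contains the baseline covariates: sex, age, BMI, race, and education". The indirect effect is alpha1 × beta2, with a bias-corrected and accelerated (BCa) bootstrap interval.

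The worked PT example puts the question to be tested as "whether greater pain catastrophizing is associated with a greater reduction in fear avoidance beliefs, which leads to greater improvement in pain interference scores". That is a statement about change in both M and Y.

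Other parts of the SAP treat the same T3 score differently:
- Section 9.1.1 defines a covariate vector "at time 2 (sex, age, BMI, race, and education) and" the T2 pain interference score. Its modifier matrix, also taken at T2 for the T3 outcome, "will have 7 total columns that correspond to the hypothesized treatment modifiers".
- Section 7.3, Table 2 ("Hypothesized light-phenotyping treatment modifiers") has eight rows and seven distinct variables, because the fibromyalgia score appears twice. The seven include the fear avoidance score (the PT mediator) and the patient experience score (the MBSR mediator). GSS-8, the acupressure mediator, is not among them.
- Section 9.2 adjusts for variables "at time point T2 (sex, age, BMI, race, education, and the baseline outcome").

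Section 9.3 is also inconsistent about the PT exposure. The expectation sentence says that people who "have lower self-perception of their own efficacy will respond better to the PT/Exercise intervention", and Table 6 lists "Pain Self-Efficacy Score". The sentence that states the test, quoted above, names pain catastrophizing.

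**The concern.** A follow-up level carries its T2 level with it. If X and the T2 mediator are correlated, alpha1 mixes the effect of X on change in M with a correlation that existed before treatment. If the T2 mediator and T2 pain interference are correlated, beta2 can differ from zero even when M has no effect on Y. Randomisation does not help, because each analysis is run inside one arm and X is not randomised there.

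Protocol 18.1.1 and 18.1.2 name the pre-treatment Experiences Questionnaire and FABQ scores as predictors of response. It is therefore reasonable to expect the T2 mediator to be related to the T3 outcome.

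At stake is which mechanisms are carried forward. An interval from the printed equations could miss or reverse a real pathway, or support an absent one, and the estimate would not show which. For PT the reader also cannot tell which sign supports the hypothesis. If X is self-efficacy, low X should go with a larger fall in fear avoidance, so the indirect effect should be positive. If X is catastrophizing, it should be negative.

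**Working it through.** The SAP gives no power or expected effect for the mediation analyses, so there is no stated figure to reproduce.

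**Inputs.** n = 102 per arm (SAP 6.1). Everything else is assumed: stability s = 0.7, the T2 correlations, and the paths a (X to change in M) and b (M to Y). Variables are standardised at T2. M2 and Y2 are the T2 values:
- M = s·M2 + a·X + e1
- Y = s·Y2 + b·(M − s·M2) + e2
- sd(e1) = sd(e2) = √(1 − 0.49) = 0.714

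In cases A and C all T2 correlations have size r on the adverse side, with X scored as self-efficacy: corr(X,M2) = corr(X,Y2) = −r and corr(M2,Y2) = +r.

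**What the printed equations estimate**
- alpha1 = a + s·corr(X,M2)
- beta2 = [cov(M,Y) − cov(X,M)·cov(X,Y)] / [var(M) − cov(X,M)²]

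*Case A, no paths (a = b = 0), r = 0.3.* alpha1 = 0.7 × (−0.3) = −0.21. beta2 = (0.147 − 0.0441) / (1 − 0.0441) = 0.108. The product is −0.023; the truth is 0.

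*Case B, X predicts change in M but M does not affect Y (a = 0.3, b = 0), corr(X,M2) = 0, corr(M2,Y2) = 0.3, corr(X,Y2) = −0.2.* alpha1 = 0.30. cov(M,Y) = 0.49 × 0.3 + 0.3 × (−0.14) = 0.105, so beta2 = (0.105 + 0.042) / (1.09 − 0.09) = 0.147. The product is +0.044; the truth is 0.

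*Case C, real pathway (a = 0.2, b = 0.3), r = 0.3.* alpha1 = 0.2 − 0.21 = −0.01 and beta2 = 0.268. The product is −0.003; the truth is 0.06.

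**Simulated intervals, n = 102.** Monte Carlo product interval, 1,500 to 2,000 runs per cell. In brackets, the SAP's BCa bootstrap, 400 runs of 1,000 resamples (standard error up to 2.5 points).

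| Case | Result counted | As printed | Both T2 values added |
|---|---|---|---|
| A, r = 0.15 | excludes 0 | 1.3% (2.3%) | 0.3% or less (1.3% or less) |
| A, r = 0.3 | excludes 0 | 9.4% (14.8%) | 0.3% or less (1.3% or less) |
| A, r = 0.4 | excludes 0 | 16.9% (27.5%) | 0.3% or less (1.3% or less) |
| B, corr(M2,Y2) = 0.15 | false support | 5–8% | 2–3% |
| B, 0.3 | false support | 22% (32%) | 2–3% (2.5–4.5%) |
| B, 0.4 | false support | 37% (50%) | 2–3% (2.5–4.5%) |
| C, r = 0.1 | detected | 9% (18%) | 62% (63%) |
| C, r = 0.3 | detected | 1.2% (1.8%) | 53% (62.5%) |

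Nearly all the exclusions in A run against the hypothesis. Those in B run with it. Repeat simulations with Monte Carlo intervals gave 8.2–8.7% for A at 0.3, 23–26% for B at 0.3, and 0.7–1.3% against 56–57.5% for C at 0.3.

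**Which T2 value does what.** Adding M2 alone gives alpha1 = a and beta2 = b in A, B and C. Adding Y2 alone gives beta2 = 0 in A and B, so either covariate largely removes the false positives there. In C, Y2 alone leaves alpha1 = 0.2 + (−0.21 + 0.063)/0.91 = 0.2 − 0.162 = 0.038, so the pathway is still mostly lost. Recovering it needs M2; Y2 then adds precision.

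**A second data model.** Here stability is 0.6, Y depends on the level of M (0.25), and X has no effect on change in M. With corr(X,M2) = −0.4 the printed product is −0.071 and 67% of BCa intervals exclude zero; with both T2 values, 5%. With all correlations at 0.2 the figures are 30% and 7%. With corr(X,M2) = +0.3 the product is +0.061, and the figures are 51% and 6%. In the −0.4 case, T2 pain interference alone leaves −0.050.

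**The case against.** The strongest reply concerns the target. X and the T2 mediator are measured at the same visit, and the documents do not order them. If X comes before the T2 mediator, the route from X through the T2 mediator to midpoint M and on to Y is a real mediated path, and adjusting for the T2 mediator removes it. In the second data model that route is −0.4 × 0.6 × 0.25 = −0.06 of the −0.071. This stands in part: for that total path the printed alpha1 is not biased. But SAP 9.3 names reduction and improvement as the target, so its wording would have to change. The beta2 of 0.108 in case A, where M has no effect on Y, would also remain.

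It is also fair that every correlation, stability and path above is assumed. At correlations of 0.15 the false-positive rates in A and B are about nominal or below in most settings, and at most 8%. The T1 entry cut of 60 on pain interference (SAP 5.4.2) could make correlations with the outcome that weak. The loss of detection in case C, however, persists at 0.1.

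Objective 3 is labelled exploratory, and SAP 7.5 reports intervals and directs findings to future study. That limits the consequence but does not answer the point.

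A reader might infer that the printed models manufacture support for the hypothesised mechanisms. The documents do not support that. If X and the T2 mediator are correlated on the adverse side, the bias runs against the hypothesis. Protocol 18.1.2 suggests such a correlation for PT only, through a related self-efficacy construct; for MBSR and acupressure it is an assumption. Nor may a reader infer that the T3 model contains the T2 mediator in all three arms, because GSS-8 is absent from Table 2.

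**Conclusion.** The concern holds for the hypothesis that SAP 9.3 states. The equations do not estimate mediation of change, and they omit T2 values that the SAP uses when it models the same T3 score elsewhere. The direction of bias cannot be settled from the documents, and its size ranges from negligible to a reversed sign across plausible T2 correlations. The most robust consequence is lost detection of a real pathway: about 1% against 53–58% at correlations of 0.3, and about 10% against 60% at 0.1. The percentages illustrate assumed inputs and are not predictions for this trial. No primary or secondary endpoint result under Objectives 1 and 2 is touched. The conflict over the PT exposure is a separate drafting error that needs no assumptions; until it is resolved, the sign of the PT indirect effect cannot be read.

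**What to change.** In SAP 9.3, add the T2 mediator and T2 PROMIS Pain Interference to both equations, in all three arms. Modelling change from T2 adjusted for the T2 values would also serve. Reconcile the PT exposure between the expectation sentence, the test sentence and Table 6, then state the predicted sign of the indirect effect for each arm. If the total path through the T2 mediator level is what is wanted, say so and rewrite the hypothesis in levels.

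The cost is SAP wording and two covariates per model. SAP Table 1 lists pain interference, FABQ, the Experiences Questionnaire and GSS-8 at T2, so no new data are needed, and Objectives 1 and 2 do not change. Bias from measurement error in the T2 values, and from the lack of a randomised contrast within an arm, remains and should be stated as a limitation.

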## 10 Safety Analyses

Even though no serious side effects are expected from the treatments, in addition to the safeguards in the SMART trial of the Research Project, the Core will monitor safety periodically with 3 interim analyses and one final analysis, using the Fleming design. The analysis will occur after each consecutive recruitment group of another 102 patients has completed their treatments (408 planned patients total under active treatments after drop-out).

Although it is highly unlikely that there will be extensive adverse events related to the study treatment that is any grade 2 or higher because these are all commonly used treatments for cLBP, we have established an alarm procedure. The alarm procedure is designed to give early warning if the rate of any related AEs, grade 2 or reaches 15% or above. The standard rate is assumed to be 10%. We will consider an alarm when more than 21, 31, 41, and 51 patients show adverse events and classify as related events and are a grade 2 or higher at the 3 interim tests and the final analysis, respectively. If the rate of adverse events is indeed at 15% or higher, the suggestion to stop the trial will be generated by this procedure at 253 treated patients or less on average. Errors of both types are set at 5%. A decision that the rate is safe will be suggested after 265 patients on average.

Events that may require the study to be discontinued or participant to be withdrawn from the study are described in the Protocol Section 18.1.6 and Section 22.

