Missing data. With high-dimensional phenotyping and the longitudinal character of the study missing data will be inevitable. Handling of missing data will include descriptive analysis of missing data patterns followed by the analysis of reasons for missingness as a nominal response using multinomial logistic regression. Sensitivity analyses will include missing data imputation by predictive-matching algorithms and missing data exclusion under a missing-at-random assumption. We do not expect more than 15% of missing data. If this assumption is not confirmed, multiple imputation approaches will be utilized.

Safety monitoring. Even though no serious side effects are expected from the treatments, in addition to the safeguards in the SMART trial of the Research Project, the Core will monitor safety periodically with 3 interim analyses and one final analysis, using the Fleming design (Fleming, T.R. (1982) One-Sample Multiple Testing Procedure for Phase II Clinical Trials, *Biometrics* 38, 143-151). The analysis will occur after each consecutive recruitment group of another 100 patients has completed their treatments (400 planned patients total under active treatments after drop-out).

Although it is highly unlikely that there will be extensive adverse events related to the study treatment that is any grade 2 or higher because these are all commonly used treatments for cLBP, we have established

an alarm procedure. The alarm procedure is designed to give early warning if the rate of any related AEs, grade 2 or reaches 15% or above. We will consider an alarm when more than 22, 32, 42, and 52 patients show adverse events and classify as related events and are a grade 2 or higher at the 3 interim tests and the final analysis, respectively. Events that may require the study to be discontinued or participant to be withdrawn from the study are described in Section 22.

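### The SAP's safety alarm cannot have both errors at 5%: counted over the 408 treated patients, the printed rule misses a 15% event rate 8.1% of the time, and the protocol prints a different rule

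*SAP*

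**What the plan says.** Both documents describe three interim safety analyses and a final one under a Fleming design.

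- **SAP section 10.** Looks follow each further 102 treated patients, 408 in all. The trigger is "We will consider an alarm when more than 21, 31, 41, and 51 patients show adverse events" that are related and of grade 2 or higher. On the null rate: "The standard rate is assumed to be 10" per cent. The unacceptable rate is 15%. On the errors: "Errors of both types are set at 5" per cent. If the rate is 15% or higher, "the suggestion to stop the trial will be generated by this procedure at 253 treated patients or less on average". For the other outcome: "A decision that the rate is safe will be suggested after 265 patients on average".
- **Protocol section 18.1.5, Safety monitoring.** For the same procedure: "We will consider an alarm when more than 22, 32, 42, and 52 patients show adverse events", and "The analysis will occur after each consecutive recruitment group of another 100 patients has completed their treatments" (400 in all). It names the alarm rate: "The alarm procedure is designed to give early warning if the rate of any related AEs, grade 2 or reaches 15% or above". It gives no standard rate, error rates or average sample sizes for this alarm.
- **Who is counted.** SAP section 7.1 times the looks on evaluable patients who have finished treatment. SAP section 7.2.3 bases safety rates on everyone who enters at T1, whatever their assignment.

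**The concern.** This alarm is the only numerical safety trigger in the two documents. SAP section 10 gives enough detail to compute its operating characteristics exactly, and the stated type II error looks too small for 10% against 15% at 408 patients. If so, whoever relies on the alarm is told that it is more sensitive than it is. The two printed threshold sets also disagree: exactly 22, 32, 42 or 52 events at the respective looks is an alarm under the SAP and not under the protocol. A promised early decision that the rate is safe cannot be carried out from a plan that gives no counts for it.

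**Working it through.** **Inputs.** From SAP section 10: look sizes 102, 204, 306, 408; p0 = 0.10; p1 = 0.15; alarm at more than 21/31/41/51, that is at r = 22, 32, 42, 52 or more. From protocol 18.1.5: look sizes 100, 200, 300, 400; alarm at 23, 33, 43, 53 or more. Assumption where stated: lower (safe) bounds of 4/19/35 or fewer at the first three looks, of the type the Fleming design would give.

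**Formula.** Let X_k be the cumulative number of patients with a qualifying event at look k. Then f_1(x) = Bin(x; 102, p), and f_k(x) = Σ f_{k−1}(y)·Bin(x − y; 102, p), summed over the counts y that continue past look k−1. P(alarm at look k) = Σ f_k(x) over x ≥ r_k.

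**Step 1: the stated 5% errors, printed SAP rule, no lower boundary.**
- At p = 0.10, P(alarm) = 0.0498. The stated 5% false-alarm rate reproduces.
- At p = 0.15, the alarm probabilities by look are 0.0477 + 0.3749 + 0.3399 + 0.1562 = 0.9187. The miss rate is 1 − 0.9187 = 0.0813, against 0.05 stated. For this rule and these 408 patients, early safe stops can only raise it.

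**Step 2: variants.**

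| Rule | False alarm at 10% | Miss at 15% |
|---|---|---|
| SAP as printed, no lower boundary | 5.0% | 8.1% |
| SAP as printed, assumed bounds 4/19/35 | 4.7% | 9.3% |
| SAP counts read as 'at least', no lower boundary | 7.0% | 6.1% |
| Protocol as printed, no lower boundary, at the SAP's rates | 2.6% | 13.9% |

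**Step 3: could any rule reach 5%/5% at 408?** By the Neyman-Pearson lemma, the best test of size 5% uses the total count over 408. Alarm at 52 or more has size 0.0423 and power 0.9130. Spending the remaining size on a count of exactly 51 means alarming there with probability (0.05 − 0.0423)/0.0159 ≈ 0.487. The miss rate is then 1 − 0.9130 − 0.487 × 0.0209 ≈ 0.077. Any rule that stops by 408 is a function of the same data and cannot do better. A single look first meets both 5% limits at 474 patients.

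**Step 4: average sample sizes.** For the printed rule with no lower boundary at p = 0.15, the average among runs that alarm is (102 × 0.0477 + 204 × 0.3749 + 306 × 0.3399 + 408 × 0.1562)/0.9187 = 249.1/0.9187 ≈ 271. Over all runs it is 249.1 + 408 × 0.0813 ≈ 282. With the assumed lower bounds the overall averages are 276 at 15% and 274 at 10%, against 253 and 265 stated.

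The stated pair is close to a different design: 400 patients, alarm at 21/31/41/51 or more, safe at 4/19/34 or fewer. That design averages 265.5 at 10% and 252.4 at a true rate of 15.44%. At 15% it averages 264.7.

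**Step 5: who is counted.** SAP section 5.1 expects approximately 500 patients at T1. Assume they accrue evenly, so that looks fall at 125, 250, 375 and 500 entrants. The printed SAP thresholds then give a 42.5% false-alarm rate and a 0.1% miss rate.

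**The case against.** Several points on the other side have force.

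- **8.1% is not a floor for every reading.** A reader might infer that the alarm misses a 15% rate at least 8.1% of the time whatever was meant. The documents do not support that. The figure needs the literal 'more than' and counts over the 408 treated patients. 'At least' gives 6.1%, at the price of a 7.0% false-alarm rate, and counting T1 entrants reverses the direction of the error.
- **The lower boundary may exist elsewhere.** Protocol section 23 refers to a separate data safety monitoring plan that was not available for this review, and section 23.2.1 has the DSMB review stopping rules in advance. What can be said is that the protocol and SAP do not print the boundary.
- **Setting 408 against 265 is unfair.** Without a lower boundary a safe decision can come only at 408, so a reader might set that against the stated 265. But the SAP names a Fleming design and promises a safe decision, so a lower boundary is implied. With the assumed bounds the gap is 274 against 265.
- **There may be an innocent origin.** The 253 and 265 figures may have been carried over from a 400-patient design, with 'more than' a one-count slip. That is inference. The 'at least' reading at 408 with the assumed bounds averages 254 among runs that alarm, close to 253, but its errors are 6.4% and 7.7%.
- **The consequence is modest.** Without a lower boundary, the printed rule reaches 95% detection at a true rate of about 15.5%.

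These points narrow the claim. None of them makes 5%/5% true at 10% and 15% with 408 patients, and none removes the conflict between the documents.

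**Conclusion.** The stated operating characteristics are wrong for the rule SAP section 10 prints. With counts over the 408 treated patients and 'more than' read literally, the false-alarm rate is 5.0% as claimed. The miss rate at 15% is 8.1%, or about 9.3% under the assumed lower bounds, against 5% stated. The 5%/5% pair is unattainable at this size, where the lowest possible miss rate is 7.7%. The averages of 253 and 265 do not belong to the printed 408-patient rule. The protocol's rule for the same procedure is different and, at the SAP's rates, less sensitive (13.9% missed). The undefined set of counted patients could move the errors further than any of this, although the 42.5% and 0.1% figures rest on an assumed 500 entrants accruing evenly.

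A reader might go on to infer that participants are left unprotected. The documents do not support that: the alarm yields a suggestion, and it sits beside DSMB review (protocol 23.2.1) and 48-hour reporting of serious events (protocol 23.1.6, SAP 10.1.5). The correction should be made, but the effect is limited.

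**What to change.** 1. Reconcile protocol 18.1.5 with SAP sections 7.1, 7.2.3 and 10, so that there is one set of thresholds, an explicit inequality, one set of look sizes and one defined group of patients for both look timing and event counts. Which thresholds to keep is for the study team and DSMB to decide.
2. Print the lower boundary at each look, or delete the 265 figure.
3. Then restate the type I error at 10%, the type II error at 15%, and the average sample sizes for that rule, labelling each average as overall or conditional on the decision. If the printed SAP rule over 408 patients is kept, the type II error to state is 8.1%, or about 9% with a Fleming-type lower boundary.

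The cost is wording in two documents and one recalculation, with no new data. The downside is a less favourable stated type II error.
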